10.4 Data Analysis

Descriptive statistics, including mean, median, standard deviations and ranges for all continuous measures will be tabulated and reported. Percentages and frequencies for all categorical measures will also be presented. Time-to-event endpoints will be reported using Kaplan-Meier estimates, with 95% CIs for median time to event.

CONFIDENTIAL

STUDY DRUG: INCB039110 (ITACITINIB)
FINAL PROTOCOL DATE: 26 OCTOBER 2021

INNOVATIONS STUDY NUMBER: BMT 29
VERSION 4

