1. INTRODUCTION

1.1 Background and Study Rationale

During the last 2 decades, the number of patients undergoing allogeneic hematopoietic stem cell transplantation (allo-HSCT) has more than doubled worldwide. Graft-versus-host disease (GVHD) remains the major hurdle to improve allo-HSCT outcome. High mortality rates are seen for patients suffering from steroid-refractory (SR) acute GVHD (aGVHD), while chronic GVHD (cGVHD) is associated with a decreased quality of life (Zeiser et al. 2015).

Depending on a number of patient- and transplant-related variables, the incidence of aGVHD ranges from 10% to 80% with symptoms usually developing 2 to 3 weeks post-transplant. It is estimated that cGVHD affects 30% to 70% of allo-HSCT recipients surviving beyond 100 days, with a median onset of 4 to 6 months following HSCT. Although cGVHD is associated with reduced relapse rates in patients transplanted for leukemia, cGVHD remains the leading cause of late death in HSCT survivors (Garnett et al. 2013).

Management of GVHD is challenging. Immunosuppression with corticosteroids forms the basis of first-line therapy in both aGVHD and cGVHD, but sustained responses are usually seen in <50% of patients and there remains no standard 2nd- and 3rd-line treatment for SR-cGVHD. While evaluation of further therapeutic options is complicated, alternative systematic therapy strategies and the identification of novel therapeutic targets are needed to improve outcomes.

A retrospective survey of 95 patients treated for SR-aGVHD and SR-cGVHD with a Janus kinase (JAK) 1/2 inhibitor, ruxolitinib, in 19 European and US transplant centers highlighted the therapeutic potential of JAK-inhibitors in the treatment of SR-GVHD. Treatment with ruxolitinib was considered safe and well tolerated in the heavily pre-treated patient population. An overall response rate (ORR) above 80% was reported for both SR-aGVHD and SR-cGVHD with median time to response being rapid (<2 weeks). Additional follow-up for patients with SR-aGVHD and SR-cGVHD reported 1-year ORRs of 62.4% and 92.7%, respectively (Zeiser et al. 2015).

A novel, potent, and selective inhibitor of the JAK family of protein tyrosine kinases (TYKs) with selectivity for JAK1, itacitinib (INCB039110 adipate), is the investigational product in this study. Itacitinib is being developed by Incyte Corporation for the treatment of GVHD, solid tumors, B-cell malignancies, myeloproliferative neoplasms, and inflammatory diseases.

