2.2 Secondary Objectives

The secondary objectives of this study are to determine the:

- Ability to either withdraw or decrease steroids to <0.5 mg/kg of methylprednisolone or equivalent
- Overall survival
- Safety and tolerability of itacitinib in patients with SR-cGVHD
- Quality of life impact using the Lee Symptom Scale from screening until the end-of-treatment (EOT) visit
- Recurrence or progression of cGVHD and
- Relapse rate of underlying malignancy.

CONFIDENTIAL

STUDY DRUG: INCB039110 (ITACITINIB)
FINAL PROTOCOL DATE: 26 OCTOBER 2021

INNOVATIONS STUDY NUMBER: BMT 29
VERSION 4

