10.4.2 Efficacy Analysis

All efficacy analyses will be performed using the Response Evaluable Analysis Set.

- ORR is defined as the proportion of patients with a cGVHD status of CR or PR after 6 months of treatment according to the NIH Consensus Criteria (Lee et al. 2015).
- Overall Survival (OS) is defined as the time from the first day of study drug administration (Day 1) to death on study. Patients who are alive will be censored at the date of last known date alive.

For ORR, the estimates and the associated 95% CIs (based on the Clopper-Pearson method) will be calculated.

For OS, a Kaplan-Meier curve will be generated and the median time to event and the associated 95% CIs will be provided.

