- j Participants will be closely monitored for any evidence of underlying disease relapse or recurrence on Day 1 of each cycle, at the EOT, and the survival follow-up visit. A formal re-staging is not required. Re-staging will be done at the Investigator's discretion. The date of malignant and non-malignant hematologic disease relapse and subsequent management should be collected on the appropriate eCRF.
- k An EOT visit should be performed for all patients who permanently discontinue study treatment (preferably within 7 days and no later than 14 days after the last treatment of study drug). If the EOT visit coincides with a regular study visit, the EOT evaluations will supersede those of that scheduled visit, and the data should be entered in the EOT visit in the eCRF (see Section 6.5).
- l A safety follow-up visit will be done 30 days (± 7 days) following end of treatment. Adverse events and SAEs must be reported for least 30 days after the last dose of study drug, and must be followed until toxicities resolve, return to baseline, or are deemed irreversible, whichever is longer (see Section 6.6.1).
- m Follow-up for survival: patients will be followed for survival after treatment has been discontinued. Patients should be contacted by telephone, email, or visit every 3 months for 1-year after their last dose of study treatment to assess for new GVHD therapy, relapse of underlying malignancy and survival status until death, withdrawal of consent, or the end of the study, whichever occurs first (see Section 6.6.2).

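### Malignancy relapse and cGVHD recurrence or progression have no estimator that accounts for death; the only time-to-event method, Kaplan-Meier, would overstate both if deaths were censored

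*Combined protocol and SAP*

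**What the plan says.** Section 2.2 (Secondary Objectives) ends its list with "Recurrence or progression of cGVHD and" and then "Relapse rate of underlying malignancy".

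Section 10.4 (Data Analysis) provides frequencies and percentages for categorical measures and, for times to event, a single sentence: "Time-to-event endpoints will be reported using Kaplan-Meier estimates, with 95% CIs for median time to event". It does not name the endpoints covered and does not say how death is handled.

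Section 10.4.2 (Efficacy Analysis) defines ORR and OS and nothing else. For OS it says: "Overall Survival (OS) is defined as the time from the first day of study drug administration (Day 1) to death on study". The only censoring rule in the plan follows: "Patients who are alive will be censored at the date of last known date alive". OS is also the only endpoint given this method by name: "For OS, a Kaplan-Meier curve will be generated and the median time to event and the associated 95% CIs will be provided". No competing-risk method appears in Section 10.

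Relapse is assessed on Day 1 of each cycle, at end of treatment and in survival follow-up. Appendix D, footnote j, asks for its timing: "The date of malignant and non-malignant hematologic disease relapse and subsequent management should be collected on the appropriate eCRF". Treatment can last up to 24 months (Appendix D, footnote a), and survival follow-up runs for 1 year after the last dose (Section 5.3).

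**The concern.** A patient who dies without relapse can no longer relapse, and the same is true of cGVHD recurrence. Kaplan-Meier with such deaths censored treats those patients as if they remained at risk. Its complement then estimates incidence in a hypothetical population in which nobody dies first, and it exceeds the proportion who actually have the event. The excess grows with follow-up.

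Death is a credible competing event here. Section 1.1 states that "cGVHD remains the leading cause of late death in HSCT survivors". The same section says that cGVHD is associated with less relapse in patients transplanted for leukemia, so readers will look closely at the relapse estimate for an immunomodulator given in this setting.

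The other route the plan leaves open is a simple proportion under the sentence on categorical measures. That counts death correctly only if everyone is followed to the same time point. Here a patient who stops early is observed for little more than 1 year, and one treated for the maximum for about 3 years (24 + 12 months).

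**Working it through.** **The plan's own figures.** The plan gives no figure for relapse, recurrence or death. Its one design figure, a width of 0.266 for the 95% CI on ORR, reproduces: 8/40 by Clopper-Pearson gives 0.0905 to 0.3565, width 0.26596. It does not bear on this point except for scale.

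**Does the general rule reach these objectives?**
- Section 10.4 covers times to event without listing them.
- Section 10.4.2 defines one such endpoint, OS, for which death is the event. Kaplan-Meier is right there.
- Section 2.2 calls relapse a rate and gives no time origin. Appendix D collects its date, so a time-to-relapse analysis is possible but not prescribed.

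The analyst is therefore left with Kaplan-Meier or a crude percentage, and neither is specified for these two objectives.

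**Size if Kaplan-Meier is used with deaths censored.** All rates are assumptions. Hazards are constant, and each annual risk is a net value, taken as if the other cause were absent.

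- Hazards: h1 = −ln(1 − annual event risk); h2 = −ln(1 − annual death risk).
- One minus Kaplan-Meier: 1 − exp(−h1·t).
- Cumulative incidence: h1/(h1 + h2) × [1 − exp(−(h1 + h2)·t)].

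For 15% relapse and 20% death per year at t = 2:
- h1 = 0.1625, h2 = 0.2231, and h1/(h1 + h2) = 0.4214.
- One minus Kaplan-Meier = 1 − 0.85² = 27.75%.
- Cumulative incidence = 0.4214 × [1 − (0.85 × 0.80)²] = 0.4214 × 0.5376 = 22.65%.
- Gap = 5.1 points; ratio 27.75/22.65 = 1.22.

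| Years | Event per year | Death per year | 1 − KM | Cumulative incidence | Gap (points) |
|---|---|---|---|---|---|
| 2 | 10% | 5% | 19.0% | 18.1% | 0.9 |
| 2 | 20% | 10% | 36.0% | 32.7% | 3.3 |
| 2 | 15% | 20% | 27.8% | 22.7% | 5.1 |
| 3 | 30% | 20% | 65.7% | 50.7% | 15.0 |

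Over a wider grid (event 5% to 40% and death 5% to 30% per year) the gap is 0.1 to 5.8 points at 1 year, 0.5 to 15.5 at 2 years and 1.0 to 23.9 at 3 years. It is zero if nobody dies before the event.

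**The case against.** A reader might infer that the plan's Kaplan-Meier rule censors deaths and so will overstate relapse. The documents do not support that. Section 10.4 contains no censoring rule, and the OS rule applies to living patients. An endpoint that counts death as an event, such as relapse-free survival, would also be reported by Kaplan-Meier without this bias. Nor does the plan class either objective as a time to event: relapse is called a rate, and cGVHD progression is a category on the response form in Appendix H. Both could be read as percentages. This stands, and it makes the point conditional.

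A reader might also take the 15-point gap as the expected error. It combines high assumed rates with the longest follow-up. Section 5.3 expects about 1 year of treatment, with a second year only for patients who benefit. The statement in Section 1.1 on late death concerns transplant survivors generally and gives no death rate for these patients. This stands too.

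The 3-year horizon does not carry over to cGVHD progression. Response is scheduled only to the end-of-treatment visit (Section 6.4, Appendix D), although Section 5.1 keeps patients who taper off in response on the assessment schedule. Survival follow-up records survival, malignancy relapse and new cGVHD therapy, not response.

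Finally, this is an exploratory single-arm study of up to 40 patients with no hypothesis test. The plan's own 95% CI at a 20% proportion is 26.6 points wide, and a 5.1-point bias is about a fifth of that (5.1/26.6 = 0.19).

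None of this supplies a suitable estimator. Both routes left open are worse than cumulative incidence, which the dates already collected for relapse and death allow.

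**Conclusion.** The point holds in conditional form. Section 10 leaves malignancy relapse and cGVHD recurrence or progression without an estimator that accounts for death, and its only time-to-event method is unsuitable for them if deaths are censored. The direction of that error is certain whenever some patients die before the event. Its size cannot be derived from the documents: in the illustrations at 2 years it runs from 0.9 points (10% and 5% per year) to 5.1 points (15% and 20% per year), under constant hazards and assumed rates.

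The consequence is limited to descriptive secondary estimates. Kaplan-Meier remains right for OS, and the primary ORR and the sample size do not change. The change is still worth making, because it puts a specific and better method where the plan has only a general one.

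**What to change.** In Sections 10.4 and 10.4.2:

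1. Restrict Kaplan-Meier to OS.
2. Define malignancy relapse as time from Day 1 to the recorded relapse date. Report cumulative incidence by the Aalen-Johansen estimator with 95% CIs, with death without relapse as the competing event. Censor patients alive without relapse at the last date on which relapse status is known.
3. Define what counts as cGVHD recurrence and as progression, and the time origin of each. Report cumulative incidence in the same way, over the period in which cGVHD is assessed (to the end-of-treatment visit, with a sentence on patients who stay on the schedule under Section 5.1). Death is a competing event.
4. State how malignancy relapse is handled in the cGVHD analysis, since it ends study treatment under Section 3.3. Treating it as a further competing event is one reasonable choice.

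The cost is a few sentences and standard software output. Relapse dates and survival status are already collected, and limiting the cGVHD analysis to the assessed period avoids any new data there.

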10.4.1 Demographics and Baseline Characteristics

Demographic and baseline disease characteristics will be summarized using descriptive statistics. Data to be tabulated will include demographic features such as age, sex, and race, as well as disease-specific characteristics.

The number and percentages of patients enrolled, treated, completed the treatment/study and withdrawn from treatment/study for any reason will be presented.

10.4.2 Efficacy Analysis

All efficacy analyses will be performed using the Response Evaluable Analysis Set.

- ORR is defined as the proportion of patients with a cGVHD status of CR or PR after 6 months of treatment according to the NIH Consensus Criteria (Lee et al. 2015).
- Overall Survival (OS) is defined as the time from the first day of study drug administration (Day 1) to death on study. Patients who are alive will be censored at the date of last known date alive.

For ORR, the estimates and the associated 95% CIs (based on the Clopper-Pearson method) will be calculated.

For OS, a Kaplan-Meier curve will be generated and the median time to event and the associated 95% CIs will be provided.

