5.1.1 Primary Efficacy Period (Cycle 1 through End of Cycle 6)

The primary efficacy period is defined as Cycle 1 through the end of Cycle 6. A cycle is 28 days. Study treatment will begin on Cycle 1 Day 1 and study drug will be dispensed on Day 1 of each cycle.

Patients will be treated for a minimum of 6 cycles, unless they meet the discontinuation criteria listed in Section 3.3).

Primary efficacy assessments will be performed on Cycle 7 Day 1, after completion of 6 cycles of treatment.

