6.4 Response Assessments

Response criteria (CR, PR, or other [unchanged, mixed response, progression]) based on the 2014 NIH Consensus Development Project on Clinical Trials in cGVHD (see Appendix H for criteria) will be assessed on Day 1 of Cycles 2 through 7; and then every odd-numbered cycle thereafter starting on Day 1 of Cycle 9, as well as the EOT visit.

Patients with GVHD progression, progression of the underlying malignancy, or unacceptable toxicity should be discontinued from the study; patients with stable GVHD or a GVHD response to therapy will continue treatment.

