6.6.2 Survival Follow Up (Every 3 Months [\pm 30 Days])

Patients who permanently discontinue the study treatment for reasons other than achieving a GVHD status of CR or PR will be followed for survival, relapse of underlying malignancy, and reporting of new cGVHD therapies approximately every 3 months for 1-year after completion of study drug, and can be contacted by telephone, email, or by a site visit.

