Any other Grade 4 toxicity	
 • Discontinue study treatment; follow-up per protocol.

ALT = alanine aminotransferase; Absolute neutrophil count = ANC; AST = aspartate aminotransferase; GVHD = graft versus host disease; LFT = liver function test; ULN = upper limit of normal.

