10.3 Analysis Population

The following analysis populations will be used:

- The Response Evaluable Analysis Set is defined as all patients with cGVHD who received at least one cycle of itacitinib and completed at least one post-baseline disease assessment.
- The Safety Analysis Set is defined as all patients who received at least one dose of itacitinib.

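### Overall survival is timed from first dose but analysed only in patients who got through Cycle 1, so early deaths drop out; the survival follow-up wording also conflicts

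*Combined protocol and SAP*

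**What the plan says.** Section 10.4.2 sets the OS clock: "Overall Survival (OS) is defined as the time from the first day of study drug administration (Day 1) to death on study". Survivors are censored when last known alive, and the summary is a Kaplan-Meier curve with the median and its 95% CI. The same section fixes the population: "All efficacy analyses will be performed using the Response Evaluable Analysis Set". OS is not set apart.

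Section 10.3 limits that set to patients with cGVHD who "received at least one cycle of itacitinib and completed at least one post-baseline disease assessment". Section 5.1.1 adds "A cycle is 28 days". Under Section 6.4, response "will be assessed on Day 1 of Cycles 2 through 7", so the first scheduled assessment falls at about Day 29 (Appendix D allows 7 days either side). Section 10.3 also defines a broader set: "The Safety Analysis Set is defined as all patients who received at least one dose of itacitinib". Section 10.4.3 uses it for safety; nothing assigns OS to it.

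On follow-up, Section 6.6.2 reads "Patients who permanently discontinue the study treatment for reasons other than achieving a GVHD status of CR or PR will be followed for survival", and also for malignancy relapse and new cGVHD treatment, about every 3 months for 1 year. Section 5.3 and Appendix D footnote m promise a year of survival follow-up with no exception by reason for stopping, although footnote m points to Section 6.6.2. Section 5.1 keeps responders who are off both itacitinib and all other immunosuppression on the Appendix D schedule.

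**The concern.** Whether a patient belongs to the OS set is decided by what happens in roughly the four weeks after the OS clock starts. That is immortal time: to be counted at all, a patient must survive, and stay on drug, through Cycle 1. Early deaths leave both the events and the denominator, and no landmark, delayed-entry or sensitivity analysis corrects for it.

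OS is a named secondary objective of a single-arm study, so its estimate can only be judged against experience outside the trial. A built-in upward shift matters for that reading, even with no test attached.

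The follow-up conflict is a separate and smaller matter. If a site works from Section 6.6.2 alone, some responders could be censored early, and that censoring may be related to prognosis.

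**Working it through.** **1. The plan's own figure.** The only design figure is the exact 95% CI width of 0.266 for a 20% response rate in 40 patients (Section 10.2). Clopper-Pearson for 8/40 gives 0.0905 to 0.3565, width 0.2660, so it reproduces. There is no corresponding figure for OS, and this one does not depend on the OS population.

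**2. Who is left out of OS.**
- *Death in Cycle 1:* fewer than 28 days of treatment, so excluded. If the one-cycle rule were read as merely starting a cycle, such a patient would usually still have no post-baseline assessment.
- *Stopping itacitinib alive in Cycle 1*, for example under the Table 2 row "Any other Grade 4 toxicity": the end-of-treatment visit (Section 6.5) supplies a response assessment, but the one-cycle rule still removes the patient. A later death found at survival follow-up then does not count.

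**3. What is estimated.** With Cycle 1 deaths removed and the clock still at Day 1, the curve estimates S(t)/S(28 days), which is never below S(t).

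**4. Size under assumed survival.** Assume a piecewise exponential with a Cycle 1 hazard m times the later hazard h, and a horizon of 365.25 days (28 + 337.25):

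- h = −ln(S12) / (337.25 + 28m)
- S28 = exp(−28·m·h)
- 12-month OS in the evaluable set = S12 / S28

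For S12 = 0.80 and m = 1: h = 0.2231/365.25 = 0.000611; S28 = exp(−0.0171) = 0.983; 0.80/0.983 = 0.814. For m = 3: h = 0.2231/421.25 = 0.000530; S28 = exp(−0.0445) = 0.956; 0.80/0.956 = 0.836.

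| True 12-month OS | Evaluable set, m = 1 | Evaluable set, m = 3 | Bias (points) |
|---|---|---|---|
| 70% | 71.9% | 75.2% | +1.9 to +5.2 |
| 80% | 81.4% | 83.6% | +1.4 to +3.6 |
| 90% | 90.7% | 91.9% | +0.7 to +1.9 |

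At 80%, expected Cycle 1 deaths, 40(1 − S28), are 0.68 (m = 1) and 1.74 (m = 3). The chance of at least one, 1 − S28^40, is 50% and 83%.

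**5. The same in counts.** With 32 of 40 alive at 12 months: 32/40 = 80.0%; one Cycle 1 death excluded, 32/39 = 82.1%; two excluded, 32/38 = 84.2%.

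**6. Patients who stop alive in Cycle 1.** Assume their 12-month survival is 60% against 80% in the rest. One such patient: all-treated OS = (39×0.80 + 0.60)/40 = 0.795. Two: (38×0.80 + 1.20)/40 = 0.790. The evaluable set reports 0.800, so it is high by 0.5 and 1.0 point. This sign depends on their prognosis being worse.

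**7. Follow-up texts side by side.**

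| Place | Who is followed |
|---|---|
| Section 5.3 | All patients |
| Appendix D, footnote m | All who discontinue |
| Section 6.6.2 | Those stopping for reasons other than CR or PR |
| Section 5.1 | CR/PR patients off itacitinib and all immunosuppression |

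A responder who stops itacitinib because of the response while still on another immunosuppressant falls under neither Section 5.1 nor Section 6.6.2. The group is narrow: by default the itacitinib taper requires corticosteroids to have been off for 8 weeks (Section 8.3), and completing planned treatment is a separate reason for stopping (Section 6.5). The documents give no basis for a figure.

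**The case against.** The strongest counter-case accepts the text and disputes its weight.

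- **The bias may be nil in this trial.** With no Cycle 1 death or exit it is zero; under a constant hazard and 80% OS that happens for deaths about half the time. This is true of one realised sample. It does not remove the upward bias in expectation.
- **The threefold hazard has no support in the documents**, and entry criteria exclude uncontrolled infection, mechanical ventilation and unstable cardiac disease. This stands: the constant-hazard range of 0.7 to 1.9 points is the more cautious figure, and the upper values show sensitivity only.
- **Early exits alive can push either way.** With four exits and 85% survival in the rest, the bias is +5.5 points if their 12-month survival is 30% and −1.5 if it is 100%. This stands, so the direction is certain only for excluded deaths.
- **The planned summary is the median, and sampling error dominates.** At 80% and a constant hazard the median is ln 2/0.000611 = 1,135 days, about 3.1 years, against at most about 3 years of follow-up (24 months of treatment plus 1 year), so it may not be reached; where it is, an exponential median shifts by 28 days. The exact CI for 32/40 is 64.4% to 90.9%, about 27 points wide. Both points are fair, but the Kaplan-Meier curve is also planned, and a systematic error is no less avoidable for being smaller than the noise.
- **The follow-up conflict is editorial.** Section 6.6.2 does not say that others are not followed, and Section 5.3 and footnote m cover the residual group. That is so, which makes it minor; the texts still disagree, and the one that describes the contacts is the restrictive one.

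**Conclusion.** The concern holds. As written, the plan estimates survival given survival through Cycle 1 and presents it as survival from first dose. If 12-month OS is 70% to 90%, the expected overstatement from excluded deaths is 0.7 to 1.9 points under a constant hazard and 1.9 to 5.2 points if the Cycle 1 hazard is threefold. In counts at 80%, it is about 2 points per excluded death. All these survival figures are assumptions. Any further effect from patients who stop alive in Cycle 1 depends on their prognosis.

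The consequence is limited. OS is secondary and descriptive, the response-rate analysis and sample size do not change, and early deaths remain visible in the safety and disposition data. The follow-up conflict is real but affects a small group of unknown size, and any bias from it cannot be quantified. The plan should be corrected on both points.

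**What to change.** 1. **OS population.** State in Section 10.4.2 that OS is analysed in the Safety Analysis Set from first dose, and limit the sentence on the Response Evaluable Analysis Set so that it does not cover OS.
2. **Survival follow-up.** Reconcile Section 6.6.2 with Sections 5.1 and 5.3 and footnote m by removing the CR/PR exception for survival and relapse contacts, so that every patient who stops itacitinib has the same 3-monthly contact for 1 year.

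The cost is two wording changes, carried through the amendment and IRB steps of Section 14.1. The Safety Analysis Set already exists, and Section 5.3 and footnote m already promise the contacts, which may be by telephone, email or visit. No new assessments or patients are needed.
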